12.1.6 Sponsor Safety Reporting Requirements in the United States

According to the final rule amending the IND safety reporting requirements under 21 CFR 312.32 and the FDA’s final guidance Safety Reporting Requirements for INDs and BA/BE Studies (December 2012), endpoints that assess disease-related mortality or major morbidity, as well other SAEs that are not study endpoints, but are known consequences of the underlying disease or condition that are anticipated to occur in the study population, should not be reported to the FDA as individual IND safety reports.

In this study, SAEs of leukemic relapse do not require individual IND safety reports. Events of febrile neutropenia are anticipated in this population and individual IND safety reports will not be submitted to the FDA. These anticipated SAEs will be reviewed periodically by Seattle Genetics’ Drug Safety Department. If, upon review, an SAE is occurring at a higher rate than that which would be expected for the study population, then an IND safety report for the SAE will be submitted to the FDA.

These safety reporting requirements apply only to the process by which the Sponsor reports SAEs to the FDA. Investigators are required to report all SAEs, including anticipated SAEs, to the Sponsor. In addition, the Sponsor will report all SAEs to international authorities as required per local regulatory reporting requirements.

13. DATA MANAGEMENT AND STATISTICAL ANALYSIS

The data management and statistical analysis of this study will be performed by an external clinical research organization (CRO) PRA Health Sciences.

13.1 Data Management

An eCRF will be used for the current study, and a data management plan will be prepared by the CRO PRA Health Sciences.

Previous and concomitant medications will be coded using the latest available WHO Drug Reference Dictionary. Coexistent diseases and AEs will be coded using the Medical Dictionary for Regulatory Activities (MedDRA).

When the database has been declared to be complete and accurate, the database will be locked. Any changes to the database after that time can only be made by written agreement between Seattle Genetics, Inc., and the PRA Health Sciences project team.

13.2 Sample Size Estimation

Phase 1 Portion (minimum of 6 subjects per cohort): Six subjects are adequate to appropriately assess the safety profiles and DLT rates of differing dose levels of vadastuximab talirine in combination with azacitidine. If the true incidence rate of DLT is 10%, the probability of considering a dose level tolerable (ie, ≤ 1 of 6 subjects experiences a DLT) will be 88.6%. If the true incidence rate of DLT is 50%, the probability of considering a dose level tolerable will be 10.9%.

Phase 2 Portion (106 subjects): A sample size of 106 subjects will provide 85% power to detect a treatment difference in ORR, assuming an ORR of 30% for azacitidine alone vs 55% for the combination of vadastuximab talirine with azacitidine, at a 2-sided 0.1 alpha level.

13.3 Statistical Analysis Plan

A Statistical Analysis Plan (SAP) will be written and finalized prior to any lock of the study database. The SAP will provide a detailed description of the statistical methods and expand on the details provided in the protocol. Additional analyses may be added. Table, listing, and figure shells will also be provided.

13.4 Randomization

During the Phase 2 Portion of the study, subjects will be randomized in a 1:1 manner to receive azacitidine with or without vadastuximab talirine, stratified by ECOG performance score (0 vs 1 or 2) and IPSS score (Intermediate-2 vs High risk). Randomization will be performed by an IXRS.

13.5 Analysis Populations

13.5.1 Intent-to-Treat Population

The intent-to-treat (ITT) population will include all subjects who are randomized in the Phase 2 Portion of the study. Subjects will be grouped according to their randomized treatment group assignment regardless of the treatment they actually received.

13.5.2 Safety Population

The safety population will include all subjects who are enrolled and received at least 1 dose of study treatment (vadastuximab talirine or azacitidine) in both portions of the study.

13.5.3 DLT-Evaluable Population

The DLT-evaluable population will include all Phase 1 subjects who have completed at least Cycle 1 of treatment (Cycle 1 of treatment is completed when the patient receives the first dose of azacitidine on Day 1 of Cycle 2) *or* discontinued study treatment because of AEs or for a safety-related reason before having had the opportunity to receive the first dose of azacitidine on Day 1 of Cycle 2. Subjects in the DLT-evaluable population will be grouped by assigned dose level.

13.5.4 Modified Intent-to-Treat Population

The modified intent-to-treat (mITT) population will include all ITT subjects who received at least 1 dose of study medication (azacitidine or vadastuximab talirine).

13.5.5 Per-Protocol Population

A per-protocol population may be defined in the SAP.

13.6 Statistical Methods

13.6.1 Missing Data

Missing data will not be imputed, with the exception of missing or partial dates; imputation rules for missing or partial dates will be specified in the SAP.

Time-to-event data will be censored as outlined in [Section 13.6.4.2](#). All other missing data will be treated as missing.

13.6.2 Demographic and Baseline Data

Demographic and baseline data will be summarized descriptively by phase and treatment arm or dose level. For continuous variables, descriptive statistics will include the mean, standard deviation (or standard error), median, range, and interquartile range. For categorical variables, descriptive statistics will include the number and percent. All demographic and baseline data will be listed.

13.6.3 Subject Disposition

The number and percent of subjects who discontinue treatment and withdraw from study and the reasons for discontinuation or withdrawal will be summarized. Disposition by the number of cycles of treatment will be summarized by phase and treatment arm or dose level.

13.6.4 Efficacy

The primary endpoint of the Phase 2 Portion is ORR, and the study will be unblinded for analysis of ORR after all subjects have completed 6 cycles of therapy or have discontinued treatment for any reason before completing 6 cycles. Data collection for the secondary efficacy endpoints and the safety and other endpoints will continue in an unblinded or partially blinded fashion until all subjects have discontinued study treatment.

13.6.4.1 Response to Treatment

Subjects will be assigned a response status based on assessments at each visit as indicated in [Table 4](#). The primary efficacy endpoint of the study is ORR, defined as the proportion of subjects who achieve any category of CR (CR and Marrow CR) or PR based on the 2006 IWG criteria for MDS [22] that are summarized in [Appendix 18.6](#). ORR will be analyzed based on the phase 2 ITT population. ORR will be assessed during the on treatment period until EOT.

The ORR will be summarized by treatment group and the corresponding 90% confidence intervals will be calculated. The treatment difference in ORR will be tested using a Cochran-Mantel-Haenszel test for the Phase 2 Portion of the study.

ORR will be summarized descriptively by dose for the subjects in the Phase 1 Portion of the study who qualified for the safety population.

13.6.4.2 Secondary Efficacy Endpoints

Time-to-event variables (DOR, PFS, and OS) will be summarized descriptively using the Kaplan-Meier estimate. Additional details will be provided in the SAP. Secondary endpoints will be assessed in the ITT population (except as indicated below).

CR Rate: Response (CR/Marrow CR, PR, ORR [CR/Marrow CR+PR], HI rate, stable disease [SD], and PD) will be summarized descriptively by treatment arm. CR rate will be summarized with 90% confidence intervals. Rate of transformation to AML will also be summarized.

DOR (for PR/CR and CR): DOR is defined as the time from first observation of response (PR+CR/Marrow CR or CR/Marrow CR) to disease progression/relapse or death from any cause, whichever occurs first. Durations will be assessed in the ITT population with a PR or CR and calculated separately for subjects with CR/Marrow CR and those with PR+CR/Marrow CR combined. For subjects with a remission without subsequent disease progression/relapse or death on study, DOR will be censored at the time of the last disease assessment demonstrating a lack of disease progression/relapse. Subjects who receive another anti-neoplastic therapy in the absence of documented progression will be censored at the time of receiving off-protocol therapy for

malignancy, EXCEPT that subjects who receive stem cell transplant in remission will continue to be followed for progression.

Progression-free Survival: PFS is defined as the time from first dose of study medication to first documentation of disease progression/relapse, or to death due to any cause, whichever occurs first. For subjects without disease progression/relapse or death on study, PFS will be censored at the time of the last on-study disease assessment demonstrating a lack of disease progression/relapse. If more than one date of progression is available, the earliest date will be used to determine PFS. Subjects who receive another anti-neoplastic therapy in the absence of documented progression will be censored at the time of receiving off-protocol therapy for malignancy, EXCEPT that subjects who receive stem cell transplant in remission will continue to be followed for progression.

Overall Survival: OS is defined as the time from first dose of study medication to death due to any cause. For subjects not known to have died at the end of the study, OS will be censored at the time the subject was last known to be alive (including follow-up data).

Efficacy endpoints will be summarized descriptively by dose for the subjects in the Phase 1 Portion of the study who qualified for the safety population.

13.6.5 Quality of Life

Data from the QLQ-C30 will be scored as recommended by the European Organization for Research and Treatment of Cancer (see [Appendix 18.7](#)) and summarized descriptively.

13.6.6 Pharmacokinetics, Immunogenicity, and Biomarkers

Estimates of selected PK parameters (vadastuximab talirine ADC and SGD-1882), incidence of ATA to vadastuximab talirine, and biomarker data (in whole blood and bone marrow, as outlined in [Section 11.4.2](#) and [Section 11.4.3](#)) will be summarized by phase and treatment arm or dose level.

13.6.7 Safety

Safety data will be summarized for the safety population separately for the Phase 1 and Phase 2 Portions by treatment arm or dose level.

Exposure to treatment will be summarized separately for vadastuximab and azacitidine. Summaries will include the duration of treatment, number of doses received, number of cycles received, number of doses interrupted and the reasons for dose interruption, the number of subjects with dose decreases for toxicity, the cumulative dose, and the relative dose intensity.

All AEs reported after initiation of treatment and pre-existing conditions that worsen after initiation of treatment will be considered treatment-emergent AEs (TEAEs). All AEs will be coded by system organ class, MedDRA preferred term, and severity grade using NCI CTCAE (v 4.03; [Appendix 18.4](#)). All recorded AEs will be included in the data listings.

The number and percent of subjects reporting all TEAEs, treatment-related AEs, SAEs, and deaths; TEAEs according to worst CTCAE grade; and AEs leading to treatment discontinuation will be summarized by preferred term and, where appropriate, system organ class. Deaths, SAEs, and AEs leading to treatment discontinuation will also be listed.

Adverse events that were considered DLTs will be listed and summarized by dose level for the DLT-evaluable population.

Summary statistics for actual values and for change from baseline will be tabulated as appropriate for laboratory results by scheduled visit. Where appropriate, laboratory results will be graded according to CTCAE 4.03, and shift tables from baseline to worst observed posttreatment grade will be presented.

All medications received during the treatment period will be considered as concomitant medications and will be coded by WHO medical dictionary and summarized.

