10. STUDY EVALUATIONS BY VISIT

A full schedule of study procedures for the screening and treatment periods is provided in [Table 4](#), and schedules of PK, immunogenicity, and biomarker assessments are given in [Table 5](#) and [Table 6](#).

Table 4: Study Schedule

	Visit Window	Baseline/Screening		Enrollment/ Randomization ^a	Each Cycle					EOT ^b	Long-term F/U
		Within 28D prior to study drug	Within 7D prior to study drug	Within 7D prior to study drug	D1	D2-6	D7	D15	D22-29	30-37 days post last dose	±2 wks
					±1D				±1D		
Baseline and Safety Assessments	Informed consent	X		Eligibility documentation submitted to Sponsor prior to study start							
	Inclusion/exclusion	X									
	Medical/MDS history	X									
	Physical examination		X								X
	Height		X								
	Weight		X			X					
	Vital signs							X ⁿ			
	Pregnancy test (serum or urine) for women of childbearing potential only		X								X
	Electrocardiogram		X								
	ECOG performance status		X			X					X
	Serum chemistry including ferritin		X			X			X ^c		X
	CBC with differential		X			X			X ^c	X ^d	X
	Urinalysis ^e		X			X ^f			X ^c		X
	Inflammatory serologies ^g		X			X ^h					X
	Specialty autoimmune serologies ⁱ		X			X ^j					X
Concomitant medications and adverse events ^l	Collect any related to study protocol procedures			Collect from predose through 30 days post last dose or EOT visit, whichever is later							
Treatment Administration	Phase 1: vadastuximab talirine ^k						X ^l				
	Phase 2: blinded study treatment ^k						X ^l				
	Azacitidine ^k				X	X	X ^l				
QoL	PRO questionnaire				X ^m					X	
PK/ATA	Blood samples for PK				See Table 5 (Phase 1 Portion) and Table 6 (Phase 2 Portion)						
	Blood samples for ATA				See Table 5 (Phase 1 Portion) and Table 6 (Phase 2 Portion)						
Biomarkers	Cytogenetics and gene mutations ⁿ	X									
	Whole blood for biomarker analysis Bone marrow for biomarker analysis ^e				See Table 5 (Phase 1 Portion) and Table 6 (Phase 2 Portion)						
Response Assessments	Bone marrow examination ^p	X							X ^d	X ^r	X ^r
	Survival status										X ^s

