12.1.3 Reporting Periods for Adverse Events and Serious Adverse Events

The safety reporting period for all AEs and SAEs is from study Day 1 (predose) through 30 days after the last dose of study treatment (vadastuximab talirine or azacitidine). However, all study protocol-related AEs are to be collected from the time of informed consent.

All SAEs that occur after the end of safety reporting period (ie, more than 30 days after the last dose of study treatment) and are considered treatment-related in the opinion of the Investigator should also be reported to the Sponsor.

SAEs will be followed until significant changes return to baseline, the event stabilizes (recovering/resolving) or is no longer considered clinically significant by the Investigator, or the subject dies or withdraws consent, or study closure. All non-serious AEs will be followed through the safety reporting period.

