12.1.4 Adverse Events of Special Interest

Hepatobiliary serious adverse events, including cases of SOS/VOD, are considered adverse events of special interest, regardless of causality. Investigators must complete a detailed “Liver

Disease Adverse Event Information Form” for all of these events. All reported adverse events of special interest will be subject to expedited reporting according to safety reporting requirements. Events of SOS/VOD that occur within 180 days of the last dose of vadastuximab talirine or blinded study drug will be reported to the Sponsor, regardless of causality. Patients who undergo subsequent allo-SCT within 180 days of the last dose of vadastuximab talirine or blinded study drug in the absence of relapse and additional therapy will be followed for SOS/VOD for 100 days post-transplant.

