### Appendix 5 Treatment Emergent Adverse Event Programming Guide

Term	Standard Definition
Treatment emergent	
Any newly occurring or worsening AE, where newly occurring means an AE that was not present at baseline. Eg, if the patient had a grade 1 headache at baseline that resolved and later had another grade 1 headache, that second headache would NOT be considered a TEAE. See below for more algorithm details.
 
Where:
 
 
1. Get first dose date/time of any study treatment-(the earliest of Azacitidine or vadastuximab talirine/placebo)
 
2. Define baseline AEs as AEs with: 
 
• an onset period of (“started before the signing of informed consent”, or “started after consent but before the first dose of any study treatment”. If the onset period of the AE is missing, then look for AE start date < first dose date (from 1). If AE start date is missing, use AE start date imputation rule.
 
 
<AND>
 
 
• a stop date that is: 
 
➢ <math>\geq</math> first dose date <OR>
 
➢ missing with outcome equal to 
 
▪ recovering/resolving (this outcome may or may not have a date with it), or
 
▪ not recovered/not resolved, or
 
▪ unknown
 
▪ Note: AEs with no outcome and missing stop dates should be queried.
 
 
 
 
 
• Note: If the event ended on Day 1 (the day of first dose) it will be considered a baseline event.
 
 
3. Define post-baseline AEs as AEs with an onset period of (“started after the first dose of any study treatment”. If the onset period of the AE is missing, then look for AE start date <math>\geq</math> first dose date (from 1). If AE start date is missing, use AE start date imputation rule.
 
4. Compare post-baseline AEs to baseline AEs using lower level term (LLT). 
 
• If terms match from baseline to post-baseline: 
 
➢ Compare CTC grades. If post-baseline CTC grade is > baseline CTC grade, then TEAE=YES. If post-baseline CTC grade is <math>\leq</math> Baseline CTC grade, then TEAE=NO.
 
 
 
• If there are no matching terms from baseline to post-baseline, then TEAE=Yes.
 
 
 

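### Treatment-emergent AEs have a start but no end, so late SAEs collected mainly on causality opinion can be counted with all-cause events

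*Protocol*

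**What the plan says.** **Definition.** Protocol 13.6.7 states: "All AEs reported after initiation of treatment and pre-existing conditions that worsen after initiation of treatment will be considered treatment-emergent AEs (TEAEs". SAP Section 5 repeats the sentence. SAP Appendix 5 turns it into an algorithm, in which treatment-emergent means "Any newly occurring or worsening AE, where newly occurring means an AE that was not present at baseline". Step 3 begins "Define post-baseline AEs as AEs with an onset period of" and goes on to require onset after the first dose of any study treatment. Step 4 removes an event whose lower level term matches a baseline event, unless the grade has risen. None of the three texts refers to the last dose.

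**Collection.** Protocol 12.1.3: "The safety reporting period for all AEs and SAEs is from study Day 1 (predose) through 30 days after the last dose of study treatment". Table 4 sets a slightly longer limit: "Collect from predose through 30 days post last dose or EOT visit, whichever is later", with the EOT visit scheduled at 30 to 37 days. For later events, 12.1.3 adds that SAEs which "are considered treatment-related in the opinion of the Investigator should also be reported to the Sponsor". Two groups escape that causality condition. Protocol 12.1.4 (also 10.4) says "Events of SOS/VOD that occur within 180 days of the last dose of vadastuximab talirine or blinded study drug will be reported to the Sponsor", whatever the cause. Protocol 12.1.2 has pregnancies reported up to 6 months after the last dose, with abortions and congenital anomalies reported as SAEs.

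**Route into the tables.** Protocol 12.1.2 has the primary event of an SAE recorded on the eCRF as well as the SAE form. SAP 9.6.1.2 then tabulates all TEAEs, treatment-emergent SAEs, grade 3-5 TEAEs and fatal TEAEs, with no date cut.

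**Blinding.** Phase 1 is open-label (Protocol 9.5.2). Phase 2 is unblinded for the ORR analysis once every subject has completed 6 cycles or stopped treatment. From then on, collection of safety data "will continue in an unblinded or partially blinded fashion until all subjects have discontinued study treatment" (Protocol 13.6.4; SAP 9.5).

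**The concern.** A percentage of subjects with an event compares arms or dose levels fairly only if events are found in the same way throughout the period counted. Here the period counted is open-ended, but the way events are found changes about a month after treatment stops. Before that point every AE is collected. After it, an SAE is collected mainly because somebody judged it to be drug-related. If that judgement is made more readily in one arm, the arms can differ in the tables with no difference in true risk. If it is made equally readily, late SAEs are still under-counted in both arms, and nothing in the table says so.

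The gap looks like an omission rather than a choice. SAP Section 5 does end the concomitant-medication window at the later of 30 days after last dose and EOT, and SAP 9.6.1.3 splits deaths at 30 days after the last vadastuximab talirine treatment. Safety is a secondary objective of both portions, and these tables are where it is compared.

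**Working it through.** **1. Is there an end date anywhere?** I compared the three definitions with the other date rules in the SAP. Protocol 13.6.7 and SAP Section 5 give only a start. Appendix 5 tests onset against first dose and grade against baseline. Appendix 4 does use last dose plus 30 days, but only to impute certain missing AE end dates, so it does not limit onset. There is no end date.

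**2. Which rule brings each kind of event in?**

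| Onset | Events collected | Causality needed? |
|---|---|---|
| First dose to 30 days after last dose (12.1.3) | All AEs and SAEs | No |
| Day 31 to EOT visit, if later (Table 4) | AEs under Table 4; related SAEs only under 12.1.3 | Sources disagree |
| After that | SAEs judged related | Yes |
| To 180 days after last vadastuximab talirine or blinded drug | SOS/VOD | No |
| To 6 months after last dose | Pregnancy outcomes that are SAEs | No |

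Under the written definition, any of these that is new or worse than baseline is a TEAE once it is on the eCRF.

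**3. How large could the distortion be?** The plan gives no late-SAE or relatedness rate, so there is no figure to reproduce, and what follows is illustration on assumptions. The only input from the documents is 106 Phase 2 subjects randomized 1:1, or 53 per arm.

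Let *L* be the true proportion of subjects with a late SAE, the same in both arms, and let *r*E and *r*C be the probabilities that it is called related in the experimental and control arms. The captured proportions are *L* × *r*E and *L* × *r*C, so the spurious difference is *L* × (*r*E − *r*C).

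| *L* | 20% vs 20% | 30% vs 20% | 40% vs 10% |
|---|---|---|---|
| 10% | 0 | 1.0 | 3.0 points (2.1 vs 0.5 subjects of 53) |
| 20% | 0 | 2.0 | 6.0 points (4.2 vs 1.1) |
| 30% | 0 | 3.0 | 9.0 points (6.4 vs 1.6) |

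For example, 0.30 × (0.40 − 0.10) = 0.09, and 53 × 0.30 × 0.40 = 6.4. The upper end is set by the assumed split: 60% versus 5% would give 5.5 to 16.5 points. With equal calling at 20% and *L* = 20%, the difference is 0, but only 4% of subjects are captured against a true 20%.

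**4. Overlap with in-window events.** The tables count subjects, so a late SAE changes an overall row only for a subject not already in it. If a share *q* of each arm already has a qualifying event, independently of late SAEs, the difference becomes *L* × (*r*E − *r*C) × (1 − *q*). The documents give no *q*. To illustrate, I borrow the febrile neutropenia frequencies that Protocol 7.2 reports in AML, 38% (combination) and 70% (monotherapy). The 9.0 points then become 9.0 × 0.62 = 5.6 and 9.0 × 0.30 = 2.7. Rows for single preferred terms would shrink less.

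**The case against.** The strongest reply is that the route into the tables is not settled. Protocol 12.1.1 has AEs recorded on the eCRF only through the end of the safety reporting period. Section 12.1.3 says that later related SAEs go to the sponsor and does not mention the eCRF. For pregnancies, 12.1.2 keeps sponsor reporting (6 months) apart from eCRF entry (30 days). This stands in part: eCRF entry of late SAEs is likely, given the general SAE instruction in 12.1.2, but it is not explicit. It does not remove the problem, because a definition without an end leaves the table content to data-entry practice.

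Second, Protocol 12.1.5 requires SAEs to be reported whatever their relationship. That section governs 24-hour reporting and sets no period. If it did extend all-cause collection, it would contradict 12.1.3.

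Third, a reader might infer that investigators will know the arm and so favour calling late events related to vadastuximab talirine. The documents do not support that. They do not say who is unblinded after the ORR analysis, late SAEs in subjects who stopped well before it are judged blind, and azacitidine is study treatment in both arms, so control-arm events can also be called related.

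Fourth, deaths are protected. SAP Section 5 takes them from the End of Study, AE and follow-up pages, and SAP 9.6.1.3 splits them at 30 days and adds 30- and 60-day mortality. This stands: the mortality comparison does not rest on the fatal-TEAE row.

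Finally, the safety tables are descriptive and all AEs are listed. That is true, but a listing does not correct a percentage.

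**Conclusion.** The point holds. The TEAE definition has no end in either document, while all-cause collection ends at about 30 to 37 days. Late SAEs entered on the eCRF would therefore join the TEAE percentages under a different rule that depends mainly on causality opinion. On the assumptions shown, the spurious between-arm difference runs from 0 (relatedness called equally) to about 9 points (30% late SAEs, 40% versus 10%), and less in overall rows. These are not estimates of what happened in this trial.

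Two stronger readings should be avoided. One is that late SAEs are collected only if called related: SOS/VOD and pregnancy outcomes are not subject to that condition. The other is that every AE after first dose becomes a TEAE: Appendix 5 drops events that match a baseline term at the same or a lower grade. No sample-size or power figure is affected.

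**What to change.** 1. In Protocol 13.6.7, SAP Section 5 and SAP Appendix 5 (step 3), limit TEAE onset to the all-cause window: from the first dose of any study treatment to the later of 30 days after the last dose of any study treatment and the EOT visit. This matches Table 4 and the SAP's concomitant-medication window. A flat 30-day cut would discard AEs that Table 4 collects whatever their cause up to the EOT visit.
2. Reconcile Protocol 12.1.3 with Table 4 so that both state the same end of collection.
3. State whether SAEs after the window are entered on the eCRF. Show later related SAEs, and SOS/VOD with onset after the window and within 180 days, in separate tables or listings outside the TEAE percentages, each labelled with its collection rule.

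The cost is one clause in three places and one or two extra outputs, with no new data. The downside is that a few late related SAEs move from the main table to a separate one, where they remain visible.
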